4.4.1.9 Proteinuria

Proteinuria is an anticipated AE with the inhibition of VEGF pathways and has been observed in cabozantinib clinical studies, and nephrotic syndrome has been reported with cabozantinib and other inhibitors of VEGF pathways. Management guidelines are provided in Table 4-7.

Treatment should be permanently discontinued in subjects who develop nephrotic syndrome (proteinuria > 3.5 grams per day in combination with hypoalbuminemia and peripheral edema [hyperlipidemia and thrombotic disease may also be present]) or any other relevant renal disease.

CONFIDENTIAL

Table 4-7: Management of Treatment-emergent Proteinuria

| Severity of Proteinuria (UPCR) | Management of Proteinuria |
|---|---|
| ≤ 1 mg/mg (≤ 113.1 mg/mmol) | 
 No change in cabozantinib treatment or monitoring |
| > 1 and < 3.5 mg/mg (> 113.1 and < 395.9 mg/mmol) | 
 Consider confirming with a 24-hour protein assessment within 7 days No change in cabozantinib treatment required if UPCR ≤ 2 mg/mg or urine protein ≤ 2 g/24 hours on 24-hour urine collection. Dose reduce or interrupt cabozantinib treatment if UPCR > 2 mg/mg on repeat UPCR testing or urine protein > 2 g/24 hours on 24-hour urine collection. Continue cabozantinib on a reduced dose if UPCR decreases to < 2 mg/mg. Consider holding cabozantinib treatment if UPCR remains > 2 mg/mg despite a dose reduction until UPCR decreases to < 2 mg/mg. Restart cabozantinib treatment at a reduced dose after a dose hold unless otherwise approved by PI. Repeat UPCR within 7 days and once per week. If UPCR < 1 mg/mg on 2 consecutive readings, UPCR monitoring can revert to protocol-specific times. (Second reading is confirmatory and can be done within 1 week of first reading.) If UPCR remains > 1 mg/mg and < 2 mg/mg for 1 month or is determined to be stable ($< 20\%$ change) for 1 month, check urine protein/creatinine per protocol or as clinically indicated. |
| ≥ 3.5 mg/mg (≥ 395.9 mg/mmol) | 
 Hold cabozantinib treatment pending repeat UPCR within 7 days and/or 24-hour urine protein. If ≥ 3.5 mg/mg on repeat UPCR, continue to hold cabozantinib treatment and check UPCR every 7 days. If UPCR decreases to < 2 mg/mg, restart cabozantinib treatment at a reduced dose and monitoring of urine protein/creatinine should continue weekly until the UPCR decreases to < 1 mg/mg. If UPCR remains > 1 mg/mg and < 2 mg/mg for 1 month or is determined to be stable ($< 20\%$ change) for 1 month, check urine protein/creatinine per protocol or as clinically indicated. |
| Nephrotic syndrome | 
 Discontinue all study treatment |

4.4.1.10 Corrected QTc Prolongation

The effect of orally administered cabozantinib 140 mg qd on QTc interval was evaluated in a placebo-controlled study in subjects with MTC. A mean increase in QTcF of 10-15 ms was observed after 4 weeks after initiating cabozantinib treatment. A concentration-QTc relationship could not be definitively established. Changes in cardiac wave form morphology or new rhythms were not observed. No cabozantinib-treated subjects in this study had a QTcF > 500 ms.

CONFIDENTIAL

Cabozantinib should be used with caution in subjects with QT prolongation risk, a history of QT interval prolongation, or who are taking antiarrhythmics or drugs known to prolong the QT interval. Concomitant treatment with strong CYP3A4 inhibitors, which may increase cabozantinib plasma concentrations, should be avoided.

If at any time on study there is an increase in QTcF to an absolute value > 500 ms or an increase of > 60 ms above baseline, two additional ECGs must be performed with intervals not less than 3 min apart within 30 min after the initial ECG.

If the average QTcF from the three ECGs is > 500 ms or increased by > 60 ms above baseline, the following actions must be taken:

- Withhold study treatment
- Immediately notify the PI
- Hospitalize symptomatic subjects (e.g., with palpitations, dizziness, syncope, orthostatic hypotension, a significant ventricular arrhythmia on ECG) for a thorough cardiology evaluation and management
- Consider cardiology consultation for asymptomatic subjects for evaluation and management
- Check electrolytes, especially magnesium, potassium and calcium; correct abnormalities as clinically indicated
- Check concomitant medications for any medication that may have contributed to QT prolongation, and if possible, discontinue these medications (<http://www.qtdrugs.org>)

Subjects with QTc prolongation and symptoms must be monitored closely until the QTc elevation and symptoms have resolved. Study treatment may be restarted at a reduced dose level if all of the following conditions are met:

- Symptoms are determined to be unrelated to the QT interval prolongation
- The QTcF value > 500 ms or increase of > 60 ms above baseline is not confirmed according to protocol procedures
- Study treatment has been interrupted through a minimum of 1 week following the return of the QTcF to ≤ 500 msec or return to ≤ 60 ms above baseline.
- QT prolongation can be unequivocally associated with an event other than cabozantinib administration and is treatable/has been resolved
- PI has reviewed all available information and has agreed to the continuation of study treatment

CONFIDENTIAL

Following reinitiation of study treatment, ECGs must be repeated weekly for 2 weeks, then every 2 weeks for 1 month, then according to the protocol-defined time points.

All study treatment must be permanently discontinued if either of the following applies:

- Cardiac evaluation confirms that symptoms are the consequence of QT interval prolongation
- Recurrence of QTcF prolongation (confirmed by ECG lab) after reinitiation of study treatment at a reduced dose

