13. Major surgery within 12 weeks before the first dose of study treatment. Complete wound healing from major surgery must have occurred 1 month before the first dose of study treatment. Minor surgery (including uncomplicated tooth extractions) within 28 days before the first dose of study treatment with complete wound healing at least 10 days before the first dose of study treatment. Subjects with clinically relevant ongoing complications from prior surgery are not eligible;
14. QTcF > 500 msec within 1 month before the first dose of study treatment:
- a. Three ECGs must be performed for eligibility determination. If the average of these three consecutive results for QTcF is ≤ 500 msec, the subject meets eligibility in this regard.
15. Pregnant or lactating females;

CONFIDENTIAL

16. Active smoker;
17. Inability to swallow intact tablets;
18. Previously identified allergy or hypersensitivity to components of the study treatment formulations;
19. Diagnosis of another malignancy within 2 years before the first dose of study treatment, except for superficial skin cancers, or localized, low grade tumors deemed cured and not treated with systemic therapy; malignancy felt by investigator to potentially affect subject survival or ability to evaluate disease response.

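### Section 4.4.1.10: the QTc recovery condition is not the complement of the hold trigger, so the one-week clock before restart can run while a hold limit is still exceeded

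*Combined protocol and SAP*

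**What the plan says.** All the rules below are in section 4.4.1.10 of the combined protocol and SAP, unless another section is named.

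- **Hold trigger.** A single ECG above either limit leads to two more. Treatment is then withheld on the mean: "If the average QTcF from the three ECGs is > 500 ms or increased by > 60 ms above baseline".
- **Restart.** "Study treatment may be restarted at a reduced dose level if all of the following conditions are met". There are five conditions. The first concerns symptoms. The other four are:
  - Condition 2: "The QTcF value > 500 ms or increase of > 60 ms above baseline is not confirmed according to protocol procedures".
  - Condition 3: treatment has been interrupted for at least one week "following the return of the QTcF to ≤ 500 msec or return to ≤ 60 ms above baseline".
  - Condition 4: "QT prolongation can be unequivocally associated with an event other than cabozantinib administration and is treatable/has been resolved".
  - Condition 5: "PI has reviewed all available information and has agreed to the continuation of study treatment".
- **After restart.** ECGs are weekly for two weeks, then less frequent. One of the two grounds for permanent discontinuation is "Recurrence of QTcF prolongation (confirmed by ECG lab) after reinitiation of study treatment at a reduced dose".
- **Entry limit (section 5.2, criterion 14a).** "If the average of these three consecutive results for QTcF is ≤ 500 msec, the subject meets eligibility in this regard". Baselines well above 440 ms are therefore eligible.

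**The concern.** A hold rule and its recovery rule should be opposites, so that a given ECG is either a reason to withhold or evidence of recovery, never both. The opposite of *above limit A or above limit B* is *at or below A and at or below B*. Condition 3 keeps the *or*.

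Condition 3 is also the only condition that sets a waiting time. If its clock can start before QTcF has cleared every limit that justifies a hold, the one-week minimum does not guarantee a week of recovery. Two investigators with identical tracings could start the clock on different days. Condition 2, which might be expected to close the gap, is itself ambiguous about which ECGs it refers to. This is a re-exposure rule for an adverse event that the protocol singles out, so patient safety is the first thing at stake.

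**Working it through.** The plan gives no figure to reproduce here; the check is one of logic. Let *b* be baseline QTcF and *q* current QTcF, both in ms.

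**Step 1. The two rules as inequalities.**
- Hold: *q* > 500 or *q* > *b* + 60, that is, *q* > min(500, *b* + 60).
- Condition 3, read literally: *q* ≤ 500 or *q* ≤ *b* + 60, that is, *q* ≤ max(500, *b* + 60).
- Both are true for *q* between the two limits, a band of width |500 − (*b* + 60)| = |440 − *b*|.

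**Step 2. Literal reading.**
- *b* = 410, *q* = 480: the rise is 480 − 410 = 70, so treatment is held; but 480 ≤ 500, so the recovery value is already met.
- *b* = 480 (eligible under 14a), *q* = 520: 520 > 500, so treatment is held; but the rise is 520 − 480 = 40, so the recovery value is already met.

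A 1-ms grid was also checked, with *b* from 360 to 500 (the top from the entry rule, the bottom assumed) and *q* from *b* to 600. It has (0 + 1 + … + 80) + (1 + 2 + … + 60) = 3240 + 1830 = 5070 pairs that are above a hold limit and also meet condition 3 taken alone. If both limits must be cleared, the count is 0. These are counts of value pairs, not of patients.

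**Step 3. Paired reading.** Suppose *return* can only mean coming back below a limit that was breached. Both examples in step 2 then drop out. A patient who breached both limits does not: *b* = 430, peak 520 (+90), now 498. The 500 ms limit has been cleared, which satisfies one side of the *or*, but 498 − 430 = 68 is still above 60.

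**Step 4. Add condition 2, applied to the current value.** A patient confirmed above either limit now fails condition 2, and the 5070 pairs fall to 0. That tests only the value on the day of restart, not when the clock began. With illustrative days:

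| | Literal reading, *b* = 410 | Paired reading, *b* = 430 |
|---|---|---|
| At hold (day 0) | 480 (+70) | 520 (+90) |
| Clock starts | day 0 (480 ≤ 500) | day 1, at 498 (+68) |
| Week completed | day 7 | day 8 |
| Last limit cleared | day 8, at 470 (+60) | day 8, at 490 (+60) |
| Conditions 2 and 3 both met | day 8 | day 8 |
| Days since last limit cleared | 0 | 0 |

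The stated minimum is 7 days after return. In both columns restart is possible, as far as conditions 2 and 3 go, with none.

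**Step 5. Apply condition 2 to the event that caused the hold.** Treatment is withheld only after the three-ECG mean has confirmed the prolongation. Condition 2 then asks that it was not confirmed. No held patient could meet it, and conditions 3 to 5 would have nothing to act on.

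**The case against.** The strongest reply is that condition 3 does not stand alone. All five conditions must hold. Condition 2, on its natural reading, bars anyone still confirmed above either limit. Condition 4 needs an unequivocal cause other than cabozantinib, and condition 5 needs the PI's agreement. Moreover, a value cannot *return* below a limit that it never exceeded, so only a double breach followed by partial recovery leaves a gap. The protocol's own data suggest that this is uncommon: in the placebo-controlled study at 140 mg daily the mean QTcF increase was 10–15 ms and no cabozantinib-treated subject exceeded 500 ms. This trial starts at 40 mg, although with erlotinib.

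Much of this stands. It rules out three stronger conclusions that a reader might draw:

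- **That a patient can be restarted while above a hold limit and so driven into a mandatory permanent stop.** With condition 2 applied to the current value, no such restart is allowed. With it applied to the triggering event, no restart is allowed at all. The stop rule also requires a lab-confirmed recurrence, and the section does not say whether prolongation that never resolved counts as one. This sequence is at most a possible consequence, for instance at a site that sets condition 2 aside because it appears impossible to meet.
- **That every patient whose baseline is not exactly 440 ms is affected.** The |440 − *b*| band follows from condition 3 alone on the literal reading. On the paired reading it matters only after both limits have been breached.
- **That the response result is at risk.** Section 8.5 rejects the combination at 2 or fewer responders of 37, so one patient could matter. But nothing in the documents gives the chance of the chain of events required.

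The reply does not restore the clock. Conditions 4 and 5 set no QTcF value or waiting time, and condition 2 on the current value says nothing about when the week begins. The reply also leaves open which meaning of condition 2 applies.

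**Conclusion.** The point holds as an inconsistency within a safety rule. The hold trigger and condition 3 are not complements. On the literal reading, and after a double breach on the paired reading, the one-week clock can start before QTcF has cleared both hold limits. The guaranteed time off treatment after full recovery can then fall from 7 days to 0. Separately, condition 2 either leaves that clock unrepaired or contradicts the confirmed hold.

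This rests on the text of section 4.4.1.10 alone. The QTcF values and days are illustrations chosen to test the wording, not expected cases. The number of patients affected is unknown and may well be small. The design's sample size, error rates and stopping boundary do not depend on it. It is worth correcting because it governs re-exposure and can be applied differently to identical ECGs.

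**What to change.** In the next amendment, reconcile four parts of section 4.4.1.10: the hold trigger, restart condition 2, restart condition 3 and the recurrence ground for permanent discontinuation. The revised text should meet four tests:

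1. No QTcF value counts as both a reason to withhold and as recovered.
2. The day on which the one-week clock starts is unambiguous, including after a breach of both limits.
3. Condition 2 states which ECGs it refers to and can be met by a patient whose hold was confirmed.
4. The recurrence rule says whether it covers prolongation that never resolved.

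The sponsor's clinicians decide the limits and the waiting time; this review takes no position on them. The cost is a short text change, with no additional scheduled ECGs and no additional patients. The downside is that some holds may last longer.

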4.4.1.11 Hypophosphatemia

Hypophosphatemia has been reported during treatment with cabozantinib. Serum phosphorus should be monitored frequently while receiving cabozantinib. Other causes of hypophosphatemia should be ruled out and/or these causes treated in accordance to standard of care. Mild to moderate hypophosphatemia should be managed by oral replacement including food that are high in phosphate (dairy items, meats, beans) and/or oral phosphate supplements in accordance to standard clinical practice guidelines.

Clinically relevant hypophosphatemia should be managed in accordance to the dose modification guidelines as outlined in Table 4-2 and Table 4-3 or as clinically indicated.

4.4.1.12 Thyroid Function Disorders

Changes in thyroid function tests (TFTs) and hypothyroidism have been reported with cabozantinib therapy and other tyrosine kinase inhibitors as a result of altered thyroid hormone regulation by mechanisms that seem to be specific for each agent.¹² Currently available data are insufficient to determine the mechanism of TFT alterations and its clinical relevance. Routine monitoring of thyroid function and assessments for signs and symptoms associated with thyroid dysfunction is recommended before initiation and during treatment. Management of thyroid dysfunction (e.g., symptomatic hypothyroidism) should follow accepted clinical practice guidelines and dose modification guidelines as outlined in Table 4-2 and 4-3.

4.4.1.13 Hemorrhagic Events

Hemorrhagic events have been reported with cabozantinib. In order to mitigate risk of severe hemorrhage, subjects should be evaluated for potential bleeding risk factors before initiating treatment and monitored for bleeding events with serial complete blood counts and physical examination while on study. Risk factors for hemorrhagic events may include (but may not be limited to) the following:

CONFIDENTIAL

- Tumor of the lung with cavitory lesions or tumor lesions which invades, encases, major blood vessels. The anatomic location and characteristics of tumor as well as the medical history must be carefully reviewed in the selection of subjects for treatment;
- Recent or concurrent radiation to the thoracic cavity;
- Active peptic ulcer disease, inflammatory GI diseases including Crohn's disease and ulcerative colitis;
- Underlying medical conditions which affect normal hemostasis (e.g., deficiencies in clotting factors and/or platelet function, or thrombocytopenia);
- Concomitant medication with anticoagulants or other drugs which affect normal hemostasis;
- History of clinically significant hemoptysis.

Treatment should be discontinued in subjects with serious and life-threatening bleeding events or recent hemoptysis (≥ 2.5 mL of red blood).

4.4.1.14 GI Perforation/Fistula and Non-GI Fistula Formation

Gastrointestinal perforation/GI fistula: After starting treatment, subjects should be monitored for early signs of GI perforation such as abdominal pain, nausea, emesis, constipation, and fever especially if known risk factors for developing GI perforation or fistula are present.

Discontinue treatment in subjects who have been diagnosed with GI perforation/fistula.

Non-GI fistula formation: Complications from radiation therapy has been identified as a possible predisposing risk factor for fistula formation in subjects undergoing treatment with cabozantinib.

Fistula should be ruled out as appropriate in cases of onset of severe mucositis or difficulty swallowing after start of therapy. Discontinue treatment and initiate appropriate management in subjects who have been diagnosed with a non-GI fistula.

Discontinue treatment in subjects who have been diagnosed with non-GI fistula.

4.4.1.15 Osteonecrosis of the Jaw

Osteonecrosis of the jaw (ONJ) has been reported in subjects treated with cabozantinib. Additional risk factors for ONJ have been identified including the use of bisphosphonates and denosumab, chemotherapy, corticosteroids, local radiotherapy, and dental or orofacial surgery procedures.

Caution should be used in subjects receiving bisphosphonates.

CONFIDENTIAL

Invasive dental procedures should be avoided. In cases where dental procedures are unavoidable, treatment should be held for at least 4 weeks prior to the procedure and resumed after complete wound healing has occurred. Bone healing may often require a protracted time.

4.4.1.16 Respiratory, Thoracic and Mediastinal Disorders

Dyspnea has been reported in clinical studies with cabozantinib and erlotinib. Cough was amongst one of the most common adverse reactions experienced by $\geq 20\%$ of subjects who took erlotinib. Symptoms should be managed according to locally accepted clinical practice including an assessment for underlying causes. Pulmonary embolism should be considered as possible causes for new onset dyspnea given the risk of thrombosis associated with inhibition of VEGF signaling. Furthermore, fistula formation and pneumonia have been reported in subjects treated with cabozantinib and should be considered as clinically indicated in subjects presenting with pulmonary symptoms.

Cases of serious ILD, including fatal cases, can occur with erlotinib treatment. Withhold treatment for acute onset of new or progressive unexplained pulmonary symptoms such as dyspnea, cough, and fever pending diagnostic evaluation. If ILD is confirmed, treatment with erlotinib should be permanently discontinued.

4.4.1.17 Renal Failure

Hepatorenal syndrome, severe acute renal failure including fatal cases, and renal insufficiency can occur with erlotinib treatment. Renal failure may arise from exacerbation of underlying baseline hepatic impairment or severe dehydration. Withhold treatment in subjects developing severe renal impairment (CTCAE version 4.03 grade 3 or 4) until renal toxicity is resolved.

4.4.1.18 Ocular Disorders

Decreased tear production, abnormal eyelash growth, keratoconjunctivitis sicca or keratitis can occur with erlotinib treatment and can lead to corneal perforation or ulceration. Discontinue erlotinib if subjects present with corneal perforation or severe ulceration. Withhold erlotinib for keratitis of NCI-CTC version 4.03 grade 3-4 or for grade 2 lasting more than 2 weeks. Withhold and consider discontinuing erlotinib for acute/worsening ocular disorders such as eye pain.

CONFIDENTIAL

4.5 Concomitant Medications and Therapies

4.5.1 Anticancer Therapy

Local intervention is discouraged unless medically unavoidable. Subjects receiving local intervention (e.g., palliative radiation) are allowed to continue to receive study treatment at the investigator's discretion.

4.5.2 Other Medications

All concomitant medications used by the subject (including prescription and over-the-counter medications, transfusions, vitamins, herbal remedies, and nutritional supplements) during the period from 28 days before the first dose of study treatment through 30 days after the date of the last dose of study treatment are to be recorded in the case report forms.

4.5.3 Allowed Therapies

- Antiemetics and antidiarrheal medications are allowed prophylactically in accordance to standard clinical practice if clinically indicated;
- Granulocyte colony-stimulating factors (G-CSF or GM-CSF) are allowed if used per clinical guidelines (e.g., American Society of Clinical Oncology [ASCO] or [European Society for Medical Oncology] ESMO guidelines);
- Drugs used to control bone loss (e.g., bisphosphonates and denosumab) are allowed if started before screening activities but may not be initiated or exchanged during the course of the study and require PI approval;
- Transfusions, hormone replacement, and short term higher doses of corticosteroids should be utilized as indicated by standard clinical practice;
- Individualized anticoagulation therapy with heparin is allowed if it can be provided safely and effectively under the following circumstances:
 - *Low dose heparins for prophylactic use* are allowed if clinically indicated and the benefit outweighs the risk per the investigator's discretion.
 - *Therapeutic doses of low molecular weight heparins (LMWH) at the time of first dose* are allowed if the subject has been on a stable dose of LMWH for at least 6 weeks, and has had no clinically significant hemorrhagic complications from the anticoagulation regimen or the tumor.
 - *Therapeutic doses of low molecular weight heparins (LMWH) after first dose* are allowed if clinically indicated (e.g., for the treatment of deep venous thrombosis), and the benefit outweighs the risk per the investigator's discretion. For

CONFIDENTIAL

management of thromboembolic complications while on study, refer to Section 4.4.1.8.

- Accepted clinical guidelines regarding appropriate management while receiving anticoagulation therapy with heparins must be followed. This includes, but is not limited to, subject education regarding potential adverse drug reactions, monitoring laboratory parameters, dose adjustments (e.g., due to kidney dysfunction);
- For restrictions on oral anticoagulants see Section 4.5.4.
- Administration of the PPI esomeprazole resulted in no clinically-relevant effect on cabozantinib plasma PK in healthy volunteers (Study XL184-018). Therefore, concomitant use of gastric pH modifying agents (i.e., PPIs, H₂ receptor antagonists, and antacids) is not contraindicated in subjects administered cabozantinib. However, co-administration of erlotinib with omeprazole decreased erlotinib AUC by 46%. Please see additional information regarding erlotinib and PPIs (omeprazole and ranitidine in Section 4.5.5). Cimetidine should be avoided with cabozantinib due to potential CYP interactions.

Potential drug interactions are summarized in Section 4.5.5.

